| 
To evaluate the safety of baricitinib + remdesivir versus dexamethasone + remdesivir as assessed by:
 
 ● Cumulative incidence of SAEs through Day 29. ● Cumulative incidence of Grade 3 and 4 clinical and/or laboratory AEs through Day 29. ● Discontinuation or temporary suspension of study product administrations (for any reason). ● Changes in white blood cell (WBC) count with differential, hemoglobin, platelets, creatinine, glucose, total bilirubin, ALT, AST, and INR on Day 1; Days 3, 5, 8, and 11 (while hospitalized); and Days 15 and 29 (if attends in-person visit or still hospitalized). | 
 ● SAEs ● Grade 3 and 4 AEs ● Incidence and number of discontinuation or temporary suspension of study product. ● WBC with differential, hemoglobin, platelets, creatinine, glucose, total bilirubin, ALT, AST, and INR on Day 1; Days 3, 5, 8, and 11 (while hospitalized); and Days 15 and 29 (if attends in-person visit or still hospitalized). |
| Exploratory Objectives and Endpoints | |
| 
Alternative Desirability of Outcome Ranking (DOOR)
 | 
 ● DOOR at Day 15 and 29 using alternative ordinal scales combining efficacy and safety (to be detailed in the statistical analysis plan) |
| Virology | |

| OBJECTIVES | ENDPOINTS (OUTCOME MEASURES) |
|--|---|
| 
To evaluate the virologic efficacy of Arm 1 as compared to Arm 2 as assessed by:
 
 Percent of subjects with SARS-CoV-2 detectable in OP sample at Days 3, 5, 8, 11, 15, and 29. Quantitative SARS-CoV-2 virus in OP sample at Days 3, 5, 8, 11, 15, and 29. Quantitative SARS-CoV-2 virus in blood at Days 3, 5, 8, and 11. | 
 Qualitative and quantitative polymerase chain reaction (PCR) for SARS-CoV-2 in OP swab on Day 1; Days 3, 5, 8, and 11 (while hospitalized); and Days 15 and 29 (if attends in-person visit or still hospitalized). Qualitative and quantitative PCR for SARS-CoV-2 in blood on Day 1; Days 3, 5, 8, and 11 (while hospitalized). |
| 
Serology To evaluate the influence of baricitinib and dexamethasone on SARS-CoV-2 antibody response.
 | 
 SARS-CoV-2 antibody titers on Day 1, 8, and 29 |

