Appendix D - ACTT-4: Baricitinib/Remdesivir vs Dexamethasone/Remdesivir

7. Lymphopenia (absolute lymphocyte count <200 cells/ μ L, $0.20 \times 10^3/\mu$ L).
8. Received five or more doses of remdesivir including the loading dose, outside of the study as treatment for COVID-19.
9. Pregnancy or breast feeding (lactating women who agree to discard breast milk from Day 1 until two weeks after the last study product is given are not excluded).
10. Allergy to any study medication.
11. Received convalescent plasma or intravenous immunoglobulin [IVIg] for COVID-19, the current illness for which they are being enrolled.
12. Received any of the following in the two weeks prior to screening as treatment of COVID-19:
 - More than one dose of baricitinib for the treatment of COVID-19;
 - Other small molecule tyrosine kinase inhibitors (e.g. imatinib, gefitinib, acalabrutinib, etc.);
 - monoclonal antibodies targeting cytokines (e.g., TNF inhibitors, anti-interleukin-1 [IL-1], anti-IL-6 [tocilizumab or sarilumab], etc.);
 - monoclonal antibodies targeting T-cells or B-cells as treatment for COVID-19.

Note: receipt of anti-SARS-CoV-2 mAb prior to enrollment (e.g. bamlanivimab) for their current COVID-19 illness is not exclusionary
13. Use of probenecid that cannot be discontinued at study enrollment.
14. Received 6 mg or more of dexamethasone po or IV (or equivalent for other glucocorticoid) in one day, or more than one day, in the 7 days prior to time of randomization. *Note: 6 mg dexamethasone dose equivalents include 40 mg prednisone, 32 mg methylprednisolone and 160 mg hydrocortisone.*
15. Received ≥ 20 mg/day of prednisone po or IV (or equivalent for other glucocorticoids) for ≥ 14 consecutive days in the 4 weeks prior to screening.
16. Have diagnosis of current active or latent tuberculosis (TB), if known, treated for less than 4 weeks with appropriate therapy (by history only, no screening required).
17. Serious infection (besides COVID-19), immunosuppressive state, or immunosuppressive medications that in the opinion of the investigator could constitute a risk when taking baricitinib or dexamethasone.
18. Have received any live vaccine (that is, live attenuated) within 4 weeks before screening, or intend to receive a live vaccine (or live attenuated) during the study. *Note: Use of non-live (inactivated) vaccinations including SARS-CoV-2 vaccine is allowed for all subjects.*

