Appendix D - ACTT-4: Baricitinib/Remdesivir vs Dexamethasone/Remdesivir

baricitinib as noted below). There should be plans on how the concomitant drugs are stopped in case of additive toxicities.

On August 23, 2020, the FDA issued an EUA for COVID-19 convalescent plasma for the treatment of hospitalized patients with COVID-19. The NIH COVID-19 Treatment Guidelines were updated on September 1, 2020 and concludes that “there are insufficient data to recommend either for or against the use of convalescent plasma for the treatment of COVID-19”. According to the NIH Guidelines and the EUA Fact Sheet for Health Care Providers, convalescent plasma should not be considered the standard of care for the treatment of patients with COVID-19. However, if a site has adopted convalescent plasma as part of their institutional standard of care for the treatment of COVID-19 patients, it is allowed as described above.

VTE prophylaxis is recommended for all patients unless there is a major contraindication such as active bleeding events or history of heparin-induced thrombosis.

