6.5.2 Prohibited Concomitant Therapy

As the study is comparing baricitinib to dexamethasone, additional baricitinib, dexamethasone and other glucocorticoids are prohibited unless the subject worsens and requires invasive mechanical ventilation (see Section 6.5.4). In addition, if oral study product is held for more than two days and the clinical condition requires, an open-label (off-study) dexamethasone or other anti-inflammatory agent may be added while the oral study product is held (Section 6.1.4). Exceptions to the steroid prohibition include: mineralocorticoids for standard indications are permitted (e.g., adrenal insufficiency, shock) and low-dose prednisone as part of immunosuppression regimen for solid organ-transplant patients is allowed (e.g., prednisone 5 mg po daily).

Strong inhibitors of organic anion transporter 3 (OAT3) such as probenecid are prohibited during the study.

Concomitant use of any other experimental treatment or off-label use of marketed medications intended as specific treatment for COVID-19 or SARS-CoV-2 infection, and not specified in the local or NIH COVID-19 Treatment Guidelines are prohibited. Specifically, use of any biologic therapy not specified on the written policy or guideline are prohibited including: monoclonal antibodies targeting cytokines (e.g., TNF inhibitors; interleukin-1[IL-1], IL-6 [tocilizumab or sarilumab]), or T-cells (e.g., abatacept); monoclonal antibodies targeting B-cells (e.g., rituximab, and including any targeting multiple cell lines including B-cells); JAK inhibitor(s) (e.g., baricitinib, imatinib, gefitinib, acalabrutinib, tofasitinib); and any type of interferon, convalescent plasma, or immunoglobulin (IgG) therapies for COVID-19. Similarly, the concomitant use of hydroxychloroquine to treat COVID-19 is prohibited unless it is included in the local institutional treatment guidelines (and even then, it is discouraged given the interaction with remdesivir).

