8. STUDY ASSESSMENTS AND PROCEDURES

8.1 Screening and Efficacy Assessments

8.1.1 Screening Procedures

Post consent screening procedures may be done over one to two calendar days (from Day -1 to Day 1). See Section 5.6.1 for allowable pre-screening procedures. However, in many cases all the screening assessments can be done in less than 24 hours. If that is the case, Day 1 pre-study product administration baseline assessments, specimen collection and the initial study product administration can occur on the same calendar day as the screening procedures.

After the informed consent, the following assessments are performed to determine eligibility:

- Confirm the positive SARS-CoV-2 test result (per inclusion criteria).
- Confirm that patient does not have a positive influenza test during the current illness for which they are being screened and possibly enrolled. Influenza testing is not required per protocol.
- Take a focused medical history, including the following information:
 - Day of onset of COVID-19 signs and symptoms.
 - Prior enrollment in ACTT-3 or ACTT-4.
 - History of vaccinations within 4 weeks before screening and planned vaccinations.
 - Exclusionary vaccine history includes any live vaccine (that is, live attenuated) within 4 weeks before screening, or intend to receive a live vaccine (or live attenuated) during the study. Note: Use of non-live (inactivated) vaccinations is allowed for all subjects including the recently EUA approved COVID-19 vaccines. Pre-study receipt of SARS-CoV-2 vaccine should be documented in the Medical History eCRF.
 - History of chronic medical conditions, including chronic oxygen requirement and/or use of CPAP or BiPAP at home, prior to onset of COVID-19. See conditions included in exclusion criteria and on the Medical History (CMX) data collection form.
 - History of medication allergies.
 - Medications and therapies for this current COVID-19 illness and history of any medication listed in the exclusion criteria. Site should identify if the patient received any dexamethasone in the 7 days prior to randomization.
 - Ask if the patient is participating in another clinical trial or plans to enroll in another clinical trial in the next 28 days.
- Women of childbearing potential should be counseled to either practice abstinence or use at least one primary form of contraception not including hormonal contraception from the time of screening through Day 29. Women should be confirmed to not be breastfeeding.

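### ACTT-4 serology: vaccine doses and antibody products given between discharge and the Day 29 sample are not recorded, so the affected subjects cannot be identified

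*Protocol*

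**What the plan says.** All references are to Appendix D (ACTT-4) of the Protocol.

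- **Objective and endpoint (section 3, exploratory, Serology).** The objective is "To evaluate the influence of baricitinib and dexamethasone on SARS-CoV-2 antibody response". The endpoint is "SARS-CoV-2 antibody titers on Day 1, 8, and 29". No assay, antigen or antibody source is named.
- **Vaccination (section 5.2, note to item 18).** "Use of non-live (inactivated) vaccinations including SARS-CoV-2 vaccine is allowed for all subjects".
- **Record of vaccination (section 8.1.1).** "Pre-study receipt of SARS-CoV-2 vaccine should be documented in the Medical History eCRF". No section asks for vaccination after enrollment.
- **Antibody products.** For monoclonal antibody, the note to item 12 of section 5.2 says "receipt of anti-SARS-CoV-2 mAb prior to enrollment (e.g. bamlanivimab) for their current COVID-19 illness is not exclusionary". Convalescent plasma or IVIg for the current illness before enrollment is exclusion 11. On study, section 6.5.1 says of plasma that "if a site has adopted convalescent plasma as part of their institutional standard of care for the treatment of COVID-19 patients, it is allowed". Section 6.5.2 otherwise lists plasma and immunoglobulin among the prohibited treatments when no written policy or guideline covers them.
- **Recording window (section 6.5.3; schedule of assessments, section 1.2).** Concomitant medications are collected from seven days before enrollment until discharge or Day 29, whichever is earlier. Section 6.5.3 makes one exception: systemic corticosteroids are followed to Day 29 even after discharge, because prolonged oral use at home could affect the study's outcomes. The schedule's medication row says to stop at discharge and shows no exception.

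**The concern.** The Day 29 titer is meant to inform a comparison of two immunosuppressive strategies on the antibody response. For a discharged subject, nearly all of the interval before that sample may lie outside the recording window. A vaccine dose in that interval is permitted and would be expected to add to the titer. An antibody product in that interval is less likely, but could be given on readmission, and section 5.6.2 notes that readmission may be to another hospital.

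How exposed subjects are analysed can be settled in an analysis plan. Who they are cannot: if the exposure is not collected during follow-up, no analysis set, sensitivity analysis or intercurrent-event strategy can be built on it afterwards.

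Exposure after discharge also follows randomization. Time at home before Day 29 depends on the discharge date, which treatment may influence, so the exposed share can differ between arms.

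**Working it through.** The protocol gives no sample size, power or usage rate for serology, so there is no stated figure to reproduce. The check sets each exposure against where it is recorded.

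| Exposure | Permitted? | Stated record |
|---|---|---|
| Monoclonal antibody before enrollment | Yes (5.2, item 12 note) | Screening history of therapies for this illness (8.1.1); prior treatments on the concomitant medication form (6.5.1) |
| Plasma or IVIg before enrollment | No (5.2, item 11) | Eligibility check |
| Vaccine before enrollment | Yes (5.2, item 18 note) | Medical history form (8.1.1) |
| Antibody product during the index stay | Plasma where site standard of care (6.5.1); otherwise only under a written policy or guideline (6.5.2) | Concomitant medications to discharge (6.5.3) |
| Vaccine after discharge, before Day 29 | Yes | None stated |
| Antibody product after discharge, before Day 29 | As during the stay | None stated; data collection on readmission is left to the manual of procedures (7.4) |

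**Which sample is affected.** Day 8 serum is drawn only if the subject is hospitalized, so it is essentially covered by the in-hospital record. Day 29 serum is drawn from discharged subjects who are seen in person or at home. Footnote 9 of the schedule lists what is collected then: clinical data, safety laboratory tests and research samples. Vaccination is not listed. The Day 60 contact (8.1.3) asks about oxygen use, disability, readmission and new diagnoses, and again not about vaccination.

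**Illustrative size.** Let d be the true between-arm difference in mean log titer, and let a share f of each arm have a Day 29 titer that carries no drug signal. Then:

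- observed difference = (1 − f)d
- factor on N for equal power, standard deviation unchanged = 1/(1 − f)²

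| f (assumed) | Observed difference | Factor on N |
|---|---|---|
| 5% | 0.95d | 1/0.9025 = 1.11 |
| 10% | 0.90d | 1/0.81 = 1.23 |
| 20% | 0.80d | 1/0.64 = 1.56 |

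This fits administered antibody. It overstates the loss for vaccination if the study drugs act on the vaccine response too, since some drug signal then remains.

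**Unequal shares.** Let the exposed shares be f₁ (baricitinib) and f₂ (dexamethasone), M the mean log titer in exposed subjects, and μ₂ the unexposed mean on dexamethasone. Then:

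observed difference = (1 − f₁)d + (f₁ − f₂)(M − μ₂).

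The second term is bias, not dilution, and can have either sign. With no record of exposure, neither f₁ nor f₂ can be estimated.

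**The case against.** The strongest reply is that this is an exploratory endpoint whose results may be reported outside the main study report, and that assay target, analysis set and handling of exposed subjects normally sit in an analysis or laboratory plan. That is right, and none of those omissions is held against the protocol here.

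A reader might infer that the permitted products make the whole serology endpoint uninterpretable. The documents do not support that, for four reasons.

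- **The assay is not fixed.** The protocol does not say that the titer captures all antibody whatever its source. Whether a given product registers depends on an assay still to be named.
- **Plasma is restricted.** It is excluded before enrollment, and on study it needs a site standard or a written policy or guideline.
- **Vaccine-induced antibody is the subject's own.** The study drugs may influence it; section 4.3.2 itself discusses vaccine response under baricitinib. The difficulty is a mixture of two responses, not an absence of signal.
- **Exposures before randomization are recorded and balanced in expectation.** They should also be reflected in the Day 1 titer, so they mainly add noise, and adjustment or exclusion needs no new data.

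It can also be said that the manual of procedures, to which section 6.5.3 refers, may collect more than the protocol states. It is not among the documents, so this cannot be checked. The protocol's own rule is to stop at discharge. What remains unanswered is the interval from discharge to the Day 29 sample.

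**Conclusion.** The point holds as a narrow data-capture gap. The protocol permits vaccination throughout, uses a Day 29 titer as an endpoint, and states no means of knowing whether a discharged subject received a vaccine dose or antibody product before that sample. The protocol accepts the same reasoning for corticosteroids, which it follows past discharge.

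The size cannot be given. The figures in the working rest on assumed shares of 5% to 20%, equal in both arms, with all drug signal lost in exposed subjects. The actual share could be lower or higher, and any difference between arms would add bias of unknown direction. The conclusion also assumes that the manual of procedures does not already extend the record.

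The effect is confined to the exploratory serology comparison at Day 29. The primary, secondary and safety analyses do not use these titers. This is a cheap improvement, not a threat to the trial's conclusions.

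**What to change.** In section 6.5.3, add SARS-CoV-2 vaccination and anti-SARS-CoV-2 antibody products (monoclonal antibody, convalescent plasma, IVIg) to the items recorded through the Day 29 contact regardless of discharge, with product and date. Amend the medication row of the schedule of assessments to match; that row should also show the corticosteroid exception that section 6.5.3 already makes. Add the question to the Day 29 contact.

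With the dates in hand, the exploratory analysis plan can set out how subjects exposed before the Day 29 sample are treated and can adjust for Day 1 titer.

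The cost is a few lines of text, a form field and one question at an existing visit. It must be in place while subjects are still being followed, because subjects who have passed Day 29 could be covered only by retrospective enquiry. No change to eligibility or permitted treatment is implied.

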4. STUDY DESIGN

4.1 Overall Design

ACTT-4 will evaluate the combination of baricitinib and remdesivir compared to dexamethasone and remdesivir. Subjects will be assessed daily while hospitalized. After the subjects are discharged from the hospital, they will have a study visit at Days 15, 22, and 29 (as applicable). For discharged subjects, it is preferred that the Day 15 and 29 visits are in person to obtain safety laboratory tests and OP swab, plasma (Day 29) and serum samples for secondary research as

Appendix D - ACTT-4: Baricitinib/Remdesivir vs Dexamethasone/Remdesivir

well as clinical outcome data. However, infection control or other restrictions may limit the ability of the subject to return to the clinic. In this case, these visits may be conducted by phone, and only clinical data will be obtained. The Day 22 visit does not have laboratory tests or collection of samples and is conducted by phone. Additionally, subjects will be contacted by phone at 2 months to assess long term efficacy and safety outcomes as an exploratory outcome.

4.2 Scientific Rationale for Study Design

This study utilizes an adaptive platform design that increases efficiency to identify safe and efficacious therapeutic agents for patients with COVID-19 during the current outbreak. In addition, the adaptive design allows for the evaluation of new therapeutic agents as they are identified and ready for testing in clinical trials. As the study is a multicenter, multinational randomized controlled study, we will be able to acquire rigorous data about the safety and efficacy of investigational therapeutic agents for COVID-19 that will lead to generalizable evidence. Randomization is essential for establishing efficacy of these new therapeutic agents. Last, collecting clinical and virologic data on enrolled subjects using a standardized timeline and collection instruments should provide valuable information about the clinical course of and morbidities associated with COVID-19 in a diverse group of hospitalized adults with confirmed SARS-CoV-2 infection.

The ACTT-4 design will specifically evaluate the contributions of blocking inflammatory pathways with the JAK inhibitor baricitinib compared with less specific, anti-inflammatory effects of dexamethasone while all subjects receive the antiviral remdesivir.

4.3 Justification for Dose

4.3.1 Justification for Dose of Remdesivir

The dose of remdesivir used in this study will be the same dose used in previous ACTT studies, and is the US FDA approved doses. The duration of dosing may be adjusted by the site according to clinical severity. The maximum number of doses to be given during hospitalization is ten doses. This includes the loading dose and all maintenance doses given during the study and pre-study if applicable.

4.3.2 Justification for Dose of Baricitinib

This study will use the same dose and duration of baricitinib that was evaluated in ACTT-2. This 4-mg daily dose of baricitinib was originally selected for use in this population of adults hospitalized with COVID-19 based on clinical data showing an inhibitory effect on cytokine signaling. In patients with RA, the 4-mg dose of baricitinib (but not lower doses) was shown to significantly reduce IL-6 levels, assessed after 12 weeks of treatment. In a vaccine response study, individuals treated with 4 mg baricitinib can mount an appropriate immune response to a pneumococcal vaccine, suggesting that transient exposure to baricitinib will not result in clinically meaningful changes to adaptive immunity (42).

4.3.3 Justification for Dose of Dexamethasone

This study will use the same dose and duration of dexamethasone that was evaluated in the RECOVERY trial, the largest and most influential study of dexamethasone in COVID-19.

5. STUDY POPULATION

Male and non-pregnant female adults ≥ 18 years of age or older with COVID-19 and who meet all eligibility criteria will be enrolled at up to approximately 100 clinical trial sites globally. The target population should reflect the community at large.

Subject Inclusion and Exclusion Criteria must be confirmed by an investigator named on the delegation log. If there is any uncertainty, the PI should make the decision on whether a potential subject is eligible for study enrollment. There is no exclusion for receipt of SARS-CoV-2 vaccine (experimental or licensed).

5.1 Inclusion Criteria

1. Hospitalized with symptoms suggestive of COVID-19.
2. Subject (or legally authorized representative) provides informed consent prior to initiation of any study procedures and understands and agrees to comply with planned study procedures.
3. Male or non-pregnant female adults ≥ 18 years of age at time of enrollment.
4. Illness of any duration and has laboratory-confirmed SARS-CoV-2 infection as determined by PCR or other commercial or public health assay (e.g. NAAT, antigen test) in any respiratory specimen or saliva ≤ 14 days prior to randomization.
5. Within the 7 days prior to randomization requiring new use of supplemental oxygen (or increased oxygen requirement if on chronic oxygen) and requires at the time of randomization low or high flow oxygen devices or use of non-invasive mechanical ventilation (ordinal scale category 5 or 6).
6. Women of childbearing potential must agree to either abstinence or use at least one primary form of contraception not including hormonal contraception from the time of screening through Day 29.
7. Agrees not to participate in another blinded clinical trial (both pharmacologic and other types of interventions) for the treatment of COVID-19 through Day 29 (see [Section 5.4](#) for more information about concurrent trial participation).

